5.8 DATA MONITORING COMMITTEE

There are no plans to utilize a data monitoring committee during this study.

5.9 ANALYSES TO BE CONDUCTED

5.9.1 General Conventions

Categorical variables will be summarized descriptively by frequencies and associated percentages. Continuous variables will be summarized descriptively by number of subjects, mean, standard deviation, median, minimum, and maximum. Confidence intervals will also be provided for procedure-related variables.

5.9.2 Disposition of Study Subjects

Subject disposition will be summarized in total and by procedure group using counts and percentages. The number and percentage of subjects completed and discontinued will be tabulated along with the specific reasons for discontinuation.

5.9.3 Demographic, Baseline, and Surgical Characteristics

Summary statistics of subject demographics (age, gender, race and ethnicity) will be presented in total and by procedure group. Similar summaries will also be provided for baseline and surgical characteristics including body mass index, surgical procedure, smoking history, ASA physical status classification, procedure duration, and additional surgical data outlined in earlier sections.

5.9.4 Primary and Secondary Endpoint Analyses

Within each procedure group, the number and percentage of subjects experiencing an occurrence of the primary endpoint will be summarized and a 95% confidence interval for each rate will be estimated. The performance goal hypotheses will be tested based on methodology as described above in Section 5.4.

The number and percentage of subjects experiencing each component of the composite endpoint will be summarized in each procedure group.

All device-related and procedure-related AEs reported during the study will be coded to MedDRA. All AEs will be summarized by MedDRA system organ class and preferred term by procedure group and in total. Separate summaries will be provided for device-related and procedure-related AEs. Serious AEs will be summarized in a similar manner.

Counts and percentages will be provided for usability data collected via surgeon questionnaire and summary statistics will be provided for the number of study devices attempted and used during the surgical procedure.

5.9.5 Plans for Interim Analyses

One interim analysis in each procedure group is planned for sample size re-estimation. Details are provided in Section 5.7 above. Study enrollment may continue while the interim analysis is ongoing.

5.9.6 Handling of Missing Data

All summaries will be performed only on subjects undergoing the scheduled procedure and only observed data will be summarized. There will be no imputation of data for early terminated subjects or for missing data within the database for the primary evaluation of the hypotheses specified above. Sensitivity analyses will be detailed in the SAP that will be designed to assess the robustness of the primary study conclusions to missing data or incomplete data on early terminated subjects.

5.9.7 Subgroup Analyses

Descriptive summaries are planned to be provided for each procedure within the lung resection group (lobectomy, segmentectomy, etc.). Subgroup analyses may be performed for additional groups pending the distributions of baseline demographic or clinical characteristics. These analyses will be exploratory, and summary statistics for the procedure-related parameters will be provided for each subgroup.

6.0 ADVERSE EVENTS

All adverse events considered unlikely, possibly, probably, or causally related to the device or the procedure will be collected during this study.

6.1 DEFINITIONS

6.1.1 Adverse Event

An AE is defined as any untoward medical occurrence, regardless of its relationship to the study device or the study procedure. An untoward medical occurrence includes any new, undesirable medical experience or worsening of a pre-existing condition, which occurs throughout the duration of the clinical study.

6.1.2 Adverse Device Effect

An adverse device effect (ADE) is an AE related to the use of a study device. This includes any AE resulting from insufficient or inadequate IFU, deployment, implantation, installation, operation, or any malfunction of the study device. An ADE may also include any event resulting from user error or from intentional misuse of the study device.

6.1.3 Serious Adverse Event

It is the Investigator's responsibility to determine the "seriousness" of a reportable AE.

A SAE is defined as an AE (as defined in Section 6.1.1) that results in any of the following:

- Death;
- A life-threatening illness or injury;
- A permanent impairment of a body structure or a body function;
- Required in-patient hospitalization or prolongation of existing hospitalization;
- Resulted in medical or surgical intervention to prevent life-threatening illness or injury or permanent impairment to a body structure or a body function; or
- Led to a fetal distress, fetal death, or a congenital abnormality or birth defect.

Note: "Death" should not be reported as an AE. The cause of death should be reported as the AE. The only exception is "Sudden Death" when the cause is unknown.

Note: Planned hospitalization for a pre-existing condition, or a procedure required by the protocol, without serious deterioration in health, is not considered a SAE.

6.1.4 Serious Adverse Device Effect (SADE)

A serious ADE (SADE) is an ADE that has resulted in any of the consequences characteristic of a SAE or that might have led to any of these consequences if suitable action had not been taken or intervention had not been made or if circumstance had been less opportune.

6.1.5 Unanticipated Serious Adverse Device Effect (USADE)

An unanticipated serious adverse device effect (USADE) is an effect which, by its nature, incidence, severity or outcome, has not been identified. An anticipated SADE is an effect which by its nature, incidence, severity, or outcome, has been identified in the IFU.

6.1.6 Pre-existing Condition

A pre-existing condition is defined as a medical condition that is present at the initiation of the study and is to be reported as part of the subject's medical history with a listed start date. Any pre-existing condition that has worsened in intensity, frequency, or the character of the condition should be recorded as a new AE on the AE eCRF, as an exacerbation of the pre-existing condition and the start date will be recorded as the time when the exacerbation occurred.

6.2 SEVERITY OF ADVERSE EVENTS

It is the Investigator's responsibility to assess the severity of an AE. A change in severity may constitute a new reportable AE.

The following guideline should be used to determine the severity of each AE:

- **MILD:** Awareness of signs or symptoms, but does not interfere with the patient's usual activity, or is a transient event that resolves without treatment and with no sequelae.
- MODERATE: A sign or symptom, which interferes with the patient's usual activity.
- SEVERE: Incapacity with inability to do work or usual activities.

6.3 RELATIONSHIP OF ADVERSE EVENTS

It is the Investigator's responsibility to assess the relationship of a reportable AE (as defined in Section 6.1.1). Only AEs considered unlikely, possibly, probably, or causally related to the study procedures or the ECHELON SLR device are to be recorded in the eCRF and reported to the Sponsor.

The following guidelines should be used in determining the relationship of an AE in the study:

- Not related Relationship to the procedures or device can be excluded when:
 - The event is not a known side effect of the product category the device belongs to or of similar devices and procedures;
 - The event has no temporal relationship with the use of the device or the procedures;
 - The event does not follow a known response pattern to the device (if the response pattern is previously known) and is biologically implausible;
 - The discontinuation of the device application or the reduction of the level activation/exposure (when clinically feasible) and reintroduction of its use (or increase of the level of activation/exposure), does not impact on the event;
 - The event involves a body site or an organ not expected to be affected by the device or the procedure;
 - The event can be attributed to another cause (e.g. an underlying or concurrent illness/clinical condition, an effect of another device, drug, treatment, or other risk factors);
 - o Harms to the subject are not clearly due to use error; or
 - To establish the non-relatedness, not all the criteria listed above might be met at the same time, depending on the type of device/procedure and the event.
- **Unlikely** The relationship with the use of the device seems not relevant and/or the event can be reasonably explained by another cause, but additional information may be obtained.
- **Possible** The relationship with the use of the device is weak but cannot be ruled out completely. Alternative causes are also possible (e.g. an underlying or concurrent illness/condition and/or an effect of another device, drug, or treatment). Cases where relatedness cannot be assessed, or no information has been obtained

should also be classified as possible.

- **Probable** The relationship with the use of the device seems relevant and/or the event cannot reasonably be explained by another cause, but additional information may be obtained.
- **Causal relationship** The event is associated with the device or with procedures beyond reasonable doubt when:
 - The event is a known side effect of the product category the device belongs to or of similar devices and procedures;
 - The event has a temporal relationship with the device uses/application or procedures;
 - The event involves a body-site or organ that:
 - The device or procedures are applied to or is adjacent to;
 - The device or procedures have an effect on;
 - The event follows a known response pattern to the medical device (if the response pattern is previously known);
 - The discontinuation of medical device application (or reduction of the level of activation/exposure) and reintroduction of its use (or increase of the level of activation/exposure), impact on the event (when clinically feasible);
 - Other possible causes (e.g. an underlying or concurrent illness/clinical condition and/or an effect of another device, drug, or treatment) have been adequately ruled out;
 - o Harm to the subject is due to error in use; or
 - To establish the relatedness, not all the criteria listed above might be met at the same time, depending on the type of device/procedure and the event.

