6.4 REPORTING PROCEDURES FOR ADVERSE EVENTS

6.4.1 Recording Adverse Events

The Investigator will record all AEs (both AEs and SAEs) considered attributable (relationship of possible, probable, causal relationship) to the study procedure or the ECHELON SLR in the source documents and eCRF.

Standard medical terminology should be used when recording AEs. In addition, the following information should be recorded:

- Onset date:
- Resolution date or date of death;
- Severity of the event;
- Indication of whether the event is serious;
- Relationship of AE to the device used in the study;
- Relationship of AE to the study procedure;
- Action taken:
- Event status; and
- Was AE anticipated or not (only for SAEs).

Data related to AEs will be collected until the event resolution, or until the event is considered stable, or until all attempts to determine the resolution of the event are

exhausted. All AEs that are unresolved at study completion (or at the last visit completed for early withdrawal subjects) will be recorded as ongoing at study end.

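### Protocol 6.3 lets novelty, or the absence of clear use error, count towards grading an adverse event Not related, and Not related events are not recorded

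*Protocol*

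**What the plan says.** Protocol 6.3 makes the investigator responsible for grading relationship and gives guidelines for five grades. The Not related grade opens with "Relationship to the procedures or device can be excluded when" and then lists considerations. Two matter here:

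- "The event is not a known side effect of the product category the device belongs to or of similar devices and procedures"
- "Harms to the subject are not clearly due to use error; or"

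The list closes with a note: "To establish the non-relatedness, not all the criteria listed above might be met at the same time". It names no minimum number and no mandatory item.

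The grade decides what is recorded. Under 6.3, "Only AEs considered unlikely, possibly, probably, or causally related to the study procedures or the ECHELON SLR device are to be recorded in the eCRF". Protocol 6.0 and SAP 8.5 give the same four-grade scope. Protocol 6.4.1 is narrower: the investigator records events "considered attributable (relationship of possible, probable, causal relationship) to the study procedure or the ECHELON SLR", which leaves out Unlikely.

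Two definitions bear on this. Protocol 6.1.5 says that an unanticipated serious adverse device effect "is an effect which, by its nature, incidence, severity or outcome, has not been identified", and refers to the IFU for what is anticipated. Protocol 6.1.2 says of an adverse device effect: "This includes any AE resulting from insufficient or inadequate IFU, deployment, implantation, installation, operation, or any malfunction of the study device". SAP Table 16 is reserved for unanticipated serious events related to the device.

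**The concern.** Safety is the primary objective, and Protocol 5.7 acknowledges that clinical data on the device are lacking. In that setting the general AE tables exist partly to show harms that nobody listed in advance. Yet an event being new to the product category is itself a listed consideration in favour of Not related. The use-error item has a similar weakness: most events after correct use are not clearly due to use error, including one caused by a malfunction, which 6.1.2 counts as a device effect.

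The consequence goes beyond the label. An event graded Not related to both device and procedure does not enter the eCRF, so it could not later be re-graded from the AE data. The study has one arm, relationship is graded by the investigator, no central re-grading is described, and no data monitoring committee is planned (Protocol 5.8, SAP 9).

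**Working it through.** No arithmetic applies: the point depends on no rate, margin or sample size. The check sets the passages side by side.

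1. **Are the two items grounds for exclusion?** Yes. Both stand in the 6.3 list under a lead-in that says when relationship can be excluded.

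2. **How many grounds are needed?** The text does not say. The word *or* after the use-error item comes before the closing note, which says that not all criteria need be met together. That fits a weighing of several criteria, and it rules out none of the smaller combinations. Novelty and absence of use error can therefore carry weight, and nothing says that they are insufficient.

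3. **What happens to the event then?**

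| Grade | Protocol 6.0, 6.3 and SAP 8.5 | Protocol 6.4.1 |
|---|---|---|
| Causal, Probable, Possible | recorded | recorded |
| Unlikely | recorded | not included |
| Not related | not recorded | not recorded |

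 Recording is triggered by relationship to the device *or* the procedure. An event graded Not related to the device but related to the procedure is still recorded. It can appear in SAP Tables 12 and 13 and be re-graded, but it is absent from the device-related Tables 14 to 16. Only an event judged unrelated to both disappears from all five tables.

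4. **Does a new device effect meet the first ground?** Often, but not always. Section 6.3 asks whether the event is known for the product category or for similar devices and procedures. Section 6.1.5 asks whether it has been identified in the IFU, by nature, incidence, severity or outcome. An event known for the category but absent from the IFU, or known but unusually severe, is unanticipated under 6.1.5 and does not meet the first ground of 6.3. The two tests coincide for an event of a wholly new type.

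5. **Does other text catch that event?** In part. Section 6.3 grades as Possible a weak link that cannot be ruled out, and any case that cannot be assessed. It does not say which grade prevails when a new event fits both Possible and the first Not related item. Under Protocol 7.1.1 a product complaint linked to a safety event requires an AE eCRF, but that route starts from an alleged device deficiency (7.0).

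6. **Is the primary endpoint exposed?** Hardly. It counts pre-listed, known complications (Protocol 2.1), so the novelty ground does not fit them. They are also collected as surgical variables (3.4.2).

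**The case against.** The strongest reply is that the list is a guideline to be weighed as a whole. The lead-in says that relationship can be excluded, not that it must be. The Causal grade in 6.3 has a mirror-image list with the same connector and the same closing note. If one item were enough in each list, a temporal link alone would make an event causal, and one event could be both Causal and Not related. A reader might infer that any single item settles the grade, so that new effects are excluded as a matter of rule. The documents do not say so, and the parallel list argues against it. This part of the reply stands.

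The reply also points to the safeguards: the Possible grade, the need to be unrelated to both device and procedure, and the complaint route, which covers devices replaced for slipping, bunching or misloading (3.4.2, 7.1.1). Unscheduled visits, concomitant procedures and medications and, where possible, cause of death are documented too, so some trace of an ungraded event may remain. Protocol 6.4.3, read alone, would have every serious event reported. These points reduce the exposure. They do not remove it: the precedence between Not related and Possible is unstated, 6.3 and 6.4.1 restrict recording by relationship for serious events too, and the other records are not AE records and do not feed Tables 12 to 16.

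The apparent overlap between Not related and Unlikely where another cause is available is partly answered by the text, since Unlikely adds that further information may be obtained.

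**Conclusion.** The point holds as a defect of wording with a real but unquantified effect. Section 6.3 permits an investigator to lean on novelty, or on the absence of clear use error, in grading an event Not related, and an event so graded for both device and procedure is not recorded. New types of effect can thus be left out of the general AE, SAE and unanticipated-event summaries. How many would be lost cannot be derived; it depends on how investigators weigh the list.

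A reader might also infer that SAP Table 16 is bound to be empty, or that the primary result is biased. Neither follows. Many unanticipated events under 6.1.5 do not meet the first ground of 6.3, and the primary endpoint rests on complications already known and separately collected.

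The conclusion assumes that sites follow 6.3 as written and have no further grading instructions outside the two documents.

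**What to change.** 1. In Protocol 6.3, remove the novelty item and the use-error item from the Not related list. Alternatively, state that neither lack of prior knowledge nor absence of use error, alone or together, establishes non-relatedness.
2. State in 6.3 that where a relationship to the device or procedure cannot be ruled out the grade is Possible, and that this prevails over the Not related list.
3. Reconcile 6.4.1 with Protocol 6.0 and 6.3 and SAP 8.5 so that Unlikely events are recorded throughout. Without this step, moving a doubtful event from Not related to Unlikely would not secure its recording under 6.4.1.

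The cost is an amendment to wording, a note to sites, and a few more events to enter and tabulate. Visits, sample size and the primary analysis do not change. SAP 8.1 analyses the gastric data first and the lung data later, so the change may still help the lung group if it comes after gastric enrolment.

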6.4 REPORTING PROCEDURES FOR ADVERSE EVENTS

6.4.1 Recording Adverse Events

The Investigator will record all AEs (both AEs and SAEs) considered attributable (relationship of possible, probable, causal relationship) to the study procedure or the ECHELON SLR in the source documents and eCRF.

Standard medical terminology should be used when recording AEs. In addition, the following information should be recorded:

- Onset date:
- Resolution date or date of death;
- Severity of the event;
- Indication of whether the event is serious;
- Relationship of AE to the device used in the study;
- Relationship of AE to the study procedure;
- Action taken:
- Event status; and
- Was AE anticipated or not (only for SAEs).

Data related to AEs will be collected until the event resolution, or until the event is considered stable, or until all attempts to determine the resolution of the event are

exhausted. All AEs that are unresolved at study completion (or at the last visit completed for early withdrawal subjects) will be recorded as ongoing at study end.

6.4.2 Reporting Adverse Events

The Investigator is required to report AEs to the Sponsor within two weeks from when the study site becomes aware of the event. All AEs must be reported on the AE eCRF and be documented in a timely manner throughout the study duration.

6.4.3 Reporting Serious Adverse Events

Any AE that the Investigator determines to be a SAE must be reported by the study site within 72 hours of becoming aware of the event to the Sponsor by completing the AE eCRF. A notification containing the pertinent data will be automatically generated by the EDC system and forwarded to the Sponsor. If applicable, supporting SAE documentation should be de-identified and provided to the Clinical Trial Leader. The report of an SAE by a study site does not constitute an admission that study personnel or the user facility (hospital/clinic) caused or contributed to the event. The study site is also responsible for submitting to the reviewing IRB per their IRB procedures.

7.0 PRODUCT COMPLAINTS

A product complaint is any written, electronic, or oral communication that alleges deficiencies related to the identity, labeling, quality, durability, reliability, safety, effectiveness, or performance of a device after it is released for distribution. A product complaint may or may not be associated with an AE/SAE.

7.1 REPORTING PRODUCT COMPLAINTS FOR MARKETED DEVICES

7.1.1 Reporting of Approved EES Marketed Devices

All product complaints related to devices in the procedure shall be documented throughout the clinical study. Product complaints related to an EES-manufactured ECHELON SLR must be reported to the Sponsor in a timely manner and no later than 24 hours after becoming aware of the event. When a sponsor representative becomes aware of a product complaint, the Product Complaint Team must be notified within 24 hours after becoming aware of the event.

The sites will report Product Complaints by completing the Product Complaint Form. If a product complaint is related to a safety event, the site must complete an AE eCRF as well. One copy of the processed form should be kept on-site and the device should be retained. Sponsor representatives will organize collection of the device for evaluation as needed.

#### **Table of Contents**

### 1 Introduction

This is the Statistical Analysis Plan (SAP) for the final analysis of data collected under Protocol ESC-2018-03. This SAP describes in detail the statistical methodology and statistical analyses for this protocol.

### 1.1 Study Objectives

The primary objective of this study is to prospectively evaluate safety in a post-market setting following use of ECHELON ENDOPATHTM Staple Line Reinforcement (ECHELON SLR) in gastric and lung resection procedures per its Instruction For Use (IFU). The secondary objective will be to capture usability data of the device.

